9.5.2 Data Monitoring Committee

An independent DMC will be established to assess safety, tolerability, and efficacy during the study, as well as to ensure the validity and scientific merit of the trial. The DMC will monitor ongoing data generated by the study at regular intervals for the duration of the study. Their role is to protect the interests of the subjects in the study and of those still to be entered, by review of

accumulating data generated in the study. If a safety concern is identified (eg, if either of the criteria are met in Section 4.5.4, Safety-related Stopping Rules), the DMC may recommend an action to the sponsor on further study conduct, including stopping the study at any time.

In addition, the DMC will review the results of the Week 24 IA and make recommendations concerning study discontinuation due to intolerance or futility, or the continued randomization of 1 or more volixibat dose groups and PBO.

The roles, responsibilities, and rules governing operation of the DMC will be discussed in full in a DMC charter. The DMC charter will define the primary responsibilities of the DMC; guide its activities, its relationship with other study components, its membership, and the purpose and timings of its meetings. It will provide the procedures for ensuring confidentiality, formal communication, and outline of the content of reports that will be provided by the DMC.

Appropriate summary statistics and data listings will be provided to the DMC by an independent statistician supported by an independent statistical reporting group not otherwise assigned to the study.

The recommendations made by the DMC to alter the conduct of the study or to stop the study will be forwarded to Shire for final decision. The implementation of any DMC recommendation is solely the responsibility of the sponsor. Shire will forward such decisions to regulatory authorities, as appropriate.

9.6 Sample Size Calculation and Power Considerations

These are the primary hypotheses that are being tested in this study:

- Null: The proportion of subjects at Week 48 with a reduction of at least 2 points without worsening of fibrosis from baseline NAS does not differ between any of the volixibat doses and PBO.
- Alternative: The proportion of subjects at Week 48 with a reduction of at least 2 points without worsening of fibrosis from baseline NAS does differ between at least one volixibat dose and PBO.

Response rates of 21% (PBO) and 45% (active) were reported in the FLINT trial ([Neuschwander-Tetri et al., 2015](#)) using the same primary end-point of reduction of NAS by at least two points (without worsening of fibrosis). Based on those response rates, 67 subjects per group completing the trial are needed for 80% power with a 10% type I error. Holm multiplicity adjustment was included in the sample size estimate.

Approximately 899 subjects will be screened to randomize 292 subjects to achieve 201 completers in the three arms (2 volixibat and 1 PBO) that continue after the IA (one dose is dropped at the IA); approximately 807 subjects will be screened to randomize 260 subjects to achieve 134 completers in the two arms (1 volixibat and 1 PBO) that continue after the IA (two

doses are dropped at the IA). After randomization of at least 80 subjects (20/treatment arm), a 24-week IA may eliminate at least one active dose group based on the criteria provided to the DMC. The sample size target for this study is 67 completers in each of the treatment groups that were not dropped at the IA (201 total if 3 arms continue, 134 if 2 arms continue). Accounting for a 20% dropout, 81 subjects will be randomized in each of the treatment groups that continue. Including the projected approximately 49 additional subjects randomized to a dose that is dropped at the IA, 292 subjects (81 for each arm that continues + 49 in the dropped arm) will be randomized if 3 arms (2 volixibat and 1 PBO) continue; 260 subject (81 for each arm that continues + 49 for each of the dropped arms) will be randomized if 2 arms (1 volixibat and 1 PBO) continue. Should the number of subjects randomized prior to the IA to a dose group that is dropped at the IA markedly deviate from the above projection, then the total number of subjects randomized will be adjusted accordingly, not to exceed approximately 324 subjects.

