MedDRA	Medical Dictionary for Regulatory Activities
MR	magnetic resonance
MRI	magnetic resonance imaging
MRS	magnetic resonance spectroscopy
MOA	mechanism of action
NAFLD	nonalcoholic fatty liver disease
NAS	NAFLD Activity Score
NASH	nonalcoholic steatohepatitis
NASH CRN	NASH Clinical Research Network
NOAEL	no observed adverse effect level
PBC	primary biliary cirrhosis

PBO	placebo
PDFF	proton density fat-fraction
PO	by mouth
POC	proof of concept
PRO	patient-reported outcome
PSC	primary sclerosing cholangitis
PT	prothrombin time
QD	once daily
RBC	red blood cell
SAE	serious adverse event
SAF	steatosis, activity, and fibrosis score
SAP	statistical analysis plan
T2DM	type 2 diabetes mellitus
T3	triiodothyronine
TA	therapeutic area
TB	total bilirubin
TEAE	treatment-emergent adverse event
TGR5	transmembrane G protein-coupled receptor
TPN	total parenteral nutrition
TSH	thyroid-stimulating hormone
TZD	thiazolidinediones
ULN	upper limit of normal
USA	United States of America
VAS	visual analogue scale

STUDY SYNOPSIS

Protocol number: SHP626-201	Drug: Volixibat potassium (SHP626)
Title of the study: A Phase 2 Double-Blind, Randomized, Placebo-controlled, Dose-finding Study to Evaluate the Safety, Tolerability and Efficacy of Volixibat Potassium, an Apical Sodium-Dependent Bile Acid Transporter Inhibitor (ASBTi) in Adults with Nonalcoholic Steatohepatitis (NASH)	
Number of subjects (total and for each treatment arm): The number of subjects screened and randomized will be dependent upon the number of dosing arms dropped following the interim analysis (IA). 
• Approximately 899 subjects will be screened to randomize 292 subjects (81 per continued dosing arm, approximately 49 per dropped dosing arm) to achieve 201 completers if three arms (2 volixibat and 1 placebo [PBO]) continue after the interim analysis (one dose is dropped after the IA).• Approximately 807 subjects will be screened to randomize 260 subjects (81 per continued dosing arm, approximately 49 per dropped dosing arm) to achieve 134 completers if two arms (1 volixibat and 1 PBO) continue after the IA (two doses are dropped after the IA).	
Investigator(s): Multicenter study	
Site(s) and Region(s): Anticipated regions: US, Canada, and EU Estimated number of sites planned: 60 to 80	
Study period (planned): July 2016 to January 2020	Clinical phase: 2

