6.2.2 Allocation of Subjects to Treatment

This is a double-blind, PBO-controlled study. The actual treatment given to individual subjects is determined by a randomization schedule.

Subject numbers are assigned to all subjects as they consent to take part in the study. Within each site (numbered uniquely within a protocol), the subject number is assigned to subjects according to the sequence of presentation for study participation.

The randomization number represents a unique number corresponding to the IP allocated to the subject, once eligibility has been determined.

Individual subject treatment is automatically assigned by the IRT.

Once a randomization number/unique identifier has been assigned, that number must not be used again if, for example, a subject is withdrawn from the study. If a randomization number/unique identifier is allocated incorrectly, the clinical research associate (CRA)/study monitor must be notified as soon as the error is discovered.

IP packaging identification numbers, separate from randomization numbers/unique identifiers, may also be assigned to subjects for specific treatment assignment as dictated by the study. In these cases, the same IP packing identification number may not be assigned to more than 1 subject.

Subjects will be equally allocated to all volixibat doses and PBO if their randomization precedes the 24 week IA. If a subject's randomization occurs after the 24 week IA, subjects will be equally allocated to all remaining volixibat doses (determined based on the results of the IA) and PBO. The randomization will be stratified by baseline T2DM and NAS ≥ 6 or NAS = {4,5}. Subjects with fibrosis stages F0 through F3 may be enrolled, but the number of F0 subjects will be capped at 88 if 1 dose is dropped after the IA and at 78 if 2 doses are dropped (approximately 30% of the total number of subjects randomized).

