9.8 Efficacy Analyses

All efficacy analyses will be based on the FAS and all statistical tests will be 2-sided hypothesis tests performed at the 10% level of significance on those doses continued after the IA, accounting for the number of doses dropped at the IA. Also, all confidence intervals will be 2-sided confidence intervals, unless otherwise stated.

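### 81 randomised per continuing arm allows for about 17% dropout, not the stated 20%, so the 67 completers per arm (201 or 134 in total) do not follow from the protocol's own figures

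*Protocol*

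**What the plan says.** Section 9.6 bases the sample size on a cited trial: "Response rates of 21% (PBO) and 45% (active) were reported in the FLINT trial". From these rates it concludes that "67 subjects per group completing the trial are needed for 80% power with a 10% type I error", and adds that "Holm multiplicity adjustment was included in the sample size estimate". Section 9.8 makes the tests two-sided at the 10% level on the doses that continue.

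Sections 3.1 and 9.6 then move from completers to randomised subjects: "Accounting for a 20% dropout, 81 subjects will be randomized in each of the treatment groups that continue". The totals are built on 81. If three arms continue, 292 are randomised (three arms of 81, plus about 49 in the dropped arm). If two continue, 260 are randomised (two arms of 81, plus about 49 in each of two dropped arms). The synopsis gives the same randomised totals and says they are meant "to achieve 201 completers if three arms" continue, or 134 completers if two continue. The synopsis does not mention the 20%.

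Two other provisions matter. Section 4.5 says that subjects who discontinue are not replaced, and waives the final biopsy for anyone stopping before Week 44. Section 9.8.1 analyses the primary endpoint in the Full Analysis Set and scores missing Week 48 data as non-response.

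**The concern.** Three stated figures cannot all hold: 81 randomised, 20% lost and 67 completing. Without replacement, nothing later in the trial closes the gap. The stated 80% power is tied to 67 completers, so anyone relying on Section 9.6 would take the completer numbers, and the power attached to them, as following from a 20% loss when they do not.

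A second question arises because power is stated for completers while the primary analysis includes dropouts as failures. The protocol does not say whether the 21% and 45% already count missing biopsies as failures, so the power of the analysis actually planned cannot be read from Section 9.6.

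**Working it through.** **Inputs.** 67 completers per arm, 20% dropout, 81 randomised per continuing arm, response rates 21% and 45%, power 80% (Sections 3.1 and 9.6); two-sided 0.10 overall (Section 9.8); Holm adjustment (Sections 9.6 and 9.8.1); no replacement (Section 4.5). With two doses continuing, the first Holm step is two-sided 0.05. With one dose continuing there is a single comparison at 0.10.

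**Step 1: the 67.** The usual two-proportion formula at two-sided 0.05 and 80% power gives 59.1 per arm, or 67.1 with a continuity correction. The corrected version is therefore the likely source of 67, although the protocol does not name its method.

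**Step 2: the 81.**
- Multiplying: 67 × 1.2 = 80.4, rounded up to 81. This reproduces the plan.
- Dividing by the fraction retained: 67 / (1 − 0.20) = 83.75, rounded up to 84. This does not.

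The superseded Amendment 3 text bound with the protocol shows the same multiplication (221 × 1.2, about 266). It suggests where the habit came from. The error itself is in the current text.

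**Step 3: what 81 delivers at 20% dropout.**
- Per arm: 81 × 0.8 = 64.8, against 67.
- Three arms: 243 × 0.8 = 194.4, against 201.
- Two arms: 162 × 0.8 = 129.6, against 134.
- Dropout at which 81 yields 67: 1 − 67/81 = 17.3%.

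The sums 3 × 81 + 49 = 292 and 2 × 81 + 98 = 260 are correct, so only the inflation step is wrong.

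**Step 4: power for one dose against placebo among completers, 21% versus 45%.** With p̄ = 0.33, power = Φ[(0.24 − c − z·√(2p̄(1−p̄)/n)) / √((0.21×0.79 + 0.45×0.55)/n)], where c = 1/n with the continuity correction and 0 without, and z = 1.96 (alpha 0.05) or 1.645 (alpha 0.10).

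| Completers per arm | Alpha | Corrected | Uncorrected |
|---|---|---|---|
| 67 | 0.05 | 79.9% | 84.8% |
| 65 | 0.05 | 78.5% | 83.7% |
| 65 | 0.10 | 86.8% | 90.5% |

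Fisher's exact test at 0.05 gives 80.8% at 67 and 79.2% at 65.

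**Step 5: the planned analysis, 81 per arm with missing counted as failure.**
- If 21% and 45% are completer rates and every dropout lacks a Week 48 biopsy, the rates become 0.8 × 21% = 16.8% and 0.8 × 45% = 36.0%. Power at 0.05 is 74% corrected and 80% uncorrected; at 0.10 it is 83% and 88%.
- If 21% and 45% already count missing biopsies as failures, no dilution applies. Power at 0.05 is 88% corrected and 91% uncorrected.

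**The case against.** The strongest objection concerns importance, and most of it stands. The shortfall is about two completers per arm, and the cost is 1 to 1.5 points of power per dose. With one dose continuing, the claim of 80% survives every version of the calculation. The figures at 0.05 are for a single dose, whereas the alternative hypothesis in Section 9.6 is that at least one dose differs. If both continuing doses truly had a 45% rate (an assumption), simulated power to reject for at least one at 65 completers per arm is about 91% corrected and 94% uncorrected.

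A reader might go further and infer that the trial is underpowered at 74%, or that it must enrol more patients. The documents do not support that. The 74% needs a continuity correction that the protocol does not specify (Section 9.8.1 names a stratified Cochran-Mantel-Haenszel test), and without it the figure is 80%. It also needs 21% and 45% to be completer-only rates, which Section 9.6 does not say; if they already include missing data, diluting them again counts dropout twice. And it needs every dropout to lack a biopsy, although Section 4.5 waives the biopsy only before Week 44.

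None of this repairs the arithmetic. The statement that 81 per arm accounts for 20% dropout and meets a target of 67 is wrong under any choice of test.

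**Conclusion.** Wrong as written, and minor to should-fix. At 20% dropout, 81 per arm leaves about 65 completers, 194 in three arms or 130 in two, instead of 67, 201 and 134. This uses only the protocol's own figures and its rule against replacement.

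The slip lowers power per dose by 1 to 1.5 points when two doses continue, which takes it just below 80% by the method that reproduces 67 and leaves it above 80% without the correction. When one dose continues, the stated 80% holds.

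The basis of the 21% and 45% is an open question, not a demonstrated deficit. At 81 per arm and alpha 0.05, power for the planned analysis is about 74% to 80% if they are completer rates and every dropout lacks a biopsy, and about 88% to 91% if missing biopsies are already counted as failures. The documents do not settle which applies.

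**What to change.** Choose one restatement:

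- In Sections 3.1 and 9.6, say that 81 per arm allows for about 17% dropout, and leave 67, 201 and 134 as they are. The synopsis needs no change, because it states no dropout rate.
- Or keep 20% and restate 65 completers per arm, with 194 or 130 in total, in Sections 3.1 and 9.6 and the synopsis, with the power in Section 9.6 adjusted to match.

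In Section 9.6, add one sentence saying whether 21% and 45% are completer rates or already count missing biopsies as failures, and give the power of the planned non-responder analysis on that basis, naming the method used.

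The cost is a few lines of text. No extra patients are needed, and the design and analysis do not change. If the sponsor prefers to keep both 67 and 20%, that takes 84 per continuing arm: 3 × 84 + 49 = 301, or 2 × 84 + 98 = 266. Both are within the ceiling of about 324.

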9.7 Study Population

The Screened Set will consist of all subjects who have signed an informed consent.

The Randomized Set will consist of all subjects in the Screened Set who have been randomized into the study.

The Safety Analysis Set will consist of all subjects who take at least 1 dose of randomized IP, and have at least 1 post-baseline safety assessment (eg, coming back for any visit, reporting of an AE or reporting the absence of AEs).

The Full Analysis Set (FAS) will consist of all subjects in the Safety Analysis Set who have at least 1 post-baseline efficacy assessment (eg, MRI, liver biopsy, serum liver-related biochemistry measurement).

The Interim Analysis Set (IAS) will consist of all subjects in the Safety Analysis Set who have at least 1 post-baseline efficacy assessment (eg, MRI, ALT biochemistry measurement) on or before the Week 24 visit at the data cut time of the IA.

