The most frequent TEAEs in the Phase 1 studies were GI and were considered mechanism-based due to elevated BA concentrations in the colon. The percentage of subjects reporting at least 1 TEAE in the GI disorders SOC generally increased with an increasing volixibat dose level (Part 1 Study TDU10632 and Study LUM002-101). Most TEAEs were mild in intensity, and none were assessed as severe.

In the multiple dose studies, the most commonly reported TEAEs in subjects (both healthy and with T2DM) who received volixibat for the longest duration of 28 days in Study LUM002-101 included diarrhea and abdominal pain. The most commonly reported TEAEs in subjects receiving 50 mg volixibat for 14 days (part 3 Study TDR10633) were diarrhea and GI pain.

Overall, there were 2 SAEs (ALT increased and retinal detachment), both of which led to the discontinuation of volixibat. In part 3 of the initial Phase 1 study (TDU10633), 1 subject dosed with 50 mg volixibat for 13 days was withdrawn from the study due to a mild TEAE (which became a SAE due to prolonged hospitalization) of ALT increased that was considered related to volixibat. The subject's ALT level returned to normal after discontinuation of volixibat. A second subject dosed with 10 mg volixibat for 12 days in Study LUM002-101 reported a moderate SAE of ablation of the retina with a bleed in the vitreous body of the right eye that was considered not related to volixibat.

Overall, 3 subjects, all dosed with 5 mg volixibat in Study LUM002-101, discontinued volixibat due to non-serious TEAEs: 1 due to a related TEAE of mild hemorrhagic diarrhea, 1 due to an unrelated TEAE of moderate Epstein-Barr virus infection, and 1 due to mild related TEAEs of diarrhea and anal erosion.

Overall, the observed AEs attributable to volixibat have been self-limited as would be expected given the local MOA of ASBT inhibition in the terminal ileum. Generally, among subjects who experienced GI TEAEs, the events have been mild and diminished over the course of treatment. Please refer to the investigator's brochure for additional information.

Volixibat is a novel drug candidate, demonstrating limited systemic exposure across species with the potential to affect important metabolic pathways associated with NASH. The overall safety, tolerability, and preliminary activity of volixibat in available clinical trials suggest that further investigation is warranted and that there is a positive benefit to risk profile.

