9.8.1 Primary Efficacy Endpoint

The primary endpoint is the binary response indicating (yes/no) whether a subject responded at Week 48 with a reduction of at least 2 points, without worsening of fibrosis, from baseline NAS.

The FAS will be used to assess the primary efficacy endpoint. The proportion of subjects at Week 48 with a reduction of at least 2 points without worsening of fibrosis from baseline NAS

will be analyzed. The difference between a volixibat dose and PBO will be tested with a stratified Cochran-Mantel-Haenzel test. The test will be stratified by presence or absence of T2DM at baseline and baseline NAS separated into two groups (NAS={4,5} or NAS={6,7,8}). Subjects with missing data for the primary efficacy endpoint at the Week 48 visit will be considered as non-responders. Holm multiplicity adjustment will be applied prior to determining statistical significance at the 0.1 level.

Analyses which explore the impact of the missing data on the primary efficacy endpoint will be conducted. These analyses may compare imputations of the missing values which favor the PBO and/or imputations which favor the active. In addition, analyses utilizing existing HFF and/or ALT data may be performed. Further, if the pattern of missing values does not appear uniformly distributed among the treatment arms, imputation method(s) based on informative missingness may also be performed. Analyses investigating the impact of missing data will be detailed in the Statistical Analysis Plan.

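### The primary analysis set leaves out randomised subjects with no post-baseline efficacy value, although the missing-equals-non-response rule would already give them an outcome

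*Protocol*

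**What the plan says.** All references are to the current protocol text (Amendment 4).

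- Section 9.8 sets the population for efficacy: "All efficacy analyses will be based on the FAS". Section 9.8.1 repeats it for the primary endpoint: "The FAS will be used to assess the primary efficacy endpoint". The binary NASH-resolution endpoint (Section 9.8.2) uses the same test and, through Section 9.8, the same set.
- Section 9.7 defines the set: "The Full Analysis Set (FAS) will consist of all subjects in the Safety Analysis Set who have at least 1 post-baseline efficacy assessment". Entry therefore has two layers. The subject must be in the Safety Analysis Set ("The Safety Analysis Set will consist of all subjects who take at least 1 dose of randomized IP", plus at least one post-baseline safety assessment) and must be one of those "who have at least 1 post-baseline efficacy assessment (eg, MRI, liver biopsy, serum liver-related biochemistry measurement"). A single liver blood test is enough.
- Section 9.8.1 sets the missing-data rule: "Subjects with missing data for the primary efficacy endpoint at the Week 48 visit will be considered as non-responders".
- Section 9.7 also defines a wider set: "The Randomized Set will consist of all subjects in the Screened Set who have been randomized into the study". The protocol gives it no efficacy analysis.
- Under Section 7.1.3 the first post-baseline liver blood test is due at Visit 3, Week 2 (Day 14 with a 3-day window). Section 4.5 asks for the Visit 9 and Visit 10 evaluations when drug is stopped, but does not require the end-of-study biopsy from those who stop before Week 44.

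**The concern.** Membership of the primary set depends on three things that happen after randomisation: a dose, a safety contact and an efficacy measurement. Such a condition is sometimes needed when a model requires a post-baseline value. It is not needed here. The endpoint is yes or no, a missing result is a no, and both stratification factors (T2DM and baseline NAS, Section 6.2.2) are known at randomisation.

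As written, two subjects who both stop drug early and have no Week 48 biopsy can be treated differently. The one with a single post-baseline blood test is a non-responder. The one without is removed from the denominator.

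At stake is the randomised comparison. Section 1.3 says "The most frequent TEAEs in the Phase 1 studies were GI and were considered mechanism-based", and adds that their frequency generally rose with dose. Section 9.5.1 has the interim analysis compare discontinuations due to adverse events, presumably gastrointestinal, between each dose and placebo. If intolerance produced more very early, permanent losses on active drug, the set would shed active non-responders and the active rate would rise. The missing-data analyses foreseen in Section 9.8.1 would not bring these subjects back, because Section 9.8 ties all efficacy analyses to the FAS.

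**Working it through.** **Inputs from the protocol (Section 9.6 unless stated).** Response 21% on placebo and 45% on active; 67 completers per group; 80% power; 10% type I error with Holm; 20% dropout; 81 randomised per continuing arm; two-sided tests (Section 9.8).

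**Assumed.** The number *k* of active subjects who fail the FAS rule is not in the documents. I take 0 to 8 of 81, with none on placebo. The upper end is extreme: planned dropout over 48 weeks is 81 − 67 = 14, or 20% × 81 ≈ 16, so 8 would be about half of it, within roughly two weeks and in one arm only.

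**1. The plan's own figure.** Two proportions, 0.21 against 0.45, two-sided α = 0.10/2 = 0.05 (first Holm step with two doses), 80% power: 60 per group without continuity correction, 68 with it. The stated 67 is reproduced within one subject.

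**2. Shift in the active rate.** With 20% dropout counted as non-response, the all-randomised rates are 0.80 × 45% = 36.0% and 0.80 × 21% = 16.8%. Active responders: 0.36 × 81 = 29.16. Under the FAS rule the active rate is 29.16/(81 − *k*), and *z* is from the pooled two-proportion test.

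| *k* (active only) | Active rate | Difference from 16.8% | *z* |
|---|---|---|---|
| 0 | 36.0% | 19.2 points | 2.77 |
| 1 | 36.5% | 19.7 | 2.82 |
| 2 | 36.9% | 20.1 | 2.87 |
| 4 | 37.9% | 21.1 | 2.98 |
| 8 | 39.9% | 23.1 | 3.20 |

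If the same number is lost in both arms, both rates rise and *z* hardly moves: with 4 lost in each arm the rates are 29.16/77 = 37.9% and 13.608/77 = 17.7%, and *z* is 2.80.

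**3. False-benefit rate.** Simulation (1,000,000 runs): 81 randomised per arm, unstratified pooled *z* test, claim of benefit if *z* > 1.96.

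- *Equal all-randomised response of 17%, early leaving counted as failure.* With active-only early loss of 0%, 2.5%, 5% or 10%, the FAS test gives 2.5%, 3.0%, 3.6% or 5.0%. The test on all randomised stays at 2.5%.
- *Same early loss in both arms.* The FAS test stays at 2.5%.
- *Equal response of 17% among those who stay.* The FAS test stays at about 2.6%. The test on all randomised falls to 2.1%, 1.7% or 1.2% at 2.5%, 5% or 10% loss.

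At the 0.10 two-sided level (one dose continuing, or the second Holm step), with 17.4% in both arms among all randomised, the rate favouring active goes from 5.1% with none lost to 6.8% with 4 lost and 9.2% with 8 lost.

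**4. Power if all 81 per arm are analysed.** With 67 of 81 completing, the rates are 45% × 67/81 = 37.2% and 21% × 67/81 = 17.4%, and power at two-sided 0.05 is 81.6%. With a full 20% dropout (36.0% against 16.8%) it is 79.7%. Either way the planned 80% is kept to within rounding.

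**The case against.** **Few subjects are affected.** One liver blood test admits a subject, and the Week 2 window opens on Day 11. Those who stop drug are asked for the Visit 9 and Visit 10 evaluations (Section 4.5), sites must make reasonable efforts to obtain them (Section 7.2), and loss to follow-up requires three contact attempts (Section 4.5.3). The first dose is given in clinic (Section 6.2.3). This stands. A reader might infer that early leavers on active drug in general vanish from the denominator; they do not. Almost all dropouts remain in the FAS as non-responders.

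**Excess loss on active is not shown.** The rule is the same in every arm. Section 1.3 also says that most events were mild, none severe, and that gastrointestinal events lessened over the course of treatment. Exclusion criterion 3 keeps out subjects with chronic diarrhea. Stopping drug is also not the same as never giving blood again. This stands too: the direction of any bias is an inference from Sections 1.3 and 9.5.1.

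**The error inflation depends on the null.** If the drug has no effect among those who stay, the FAS test keeps its level. The inflated figures apply only when early leaving is itself a failure. That is the view taken by the plan's non-responder rule for every other dropout, but it is a choice and must be stated.

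**The text does not contradict itself.** It may be tempting to say that the FAS breaches the plan's own non-responder rule. Section 9.8.1 names the FAS first and then imputes within it. No passage promises imputation for all randomised subjects, so the rule is narrow rather than broken.

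What the objection does not supply is a reason for the exclusion.

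**Conclusion.** The point holds as a modest, conditional weakness. The protocol fixes a primary set that depends on post-randomisation events, for an endpoint that needs no such condition, and leaves unused a set that would avoid it.

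Each active subject lost, with none lost on placebo, adds about half a point to the active rate. At 4 of 81 the rise is 1.9 points and at 8 it is 3.9, the latter an extreme case. The rise in the false-benefit rate (2.5% to about 3.0%, 3.6% or 5.0%) rests on three assumptions: loss on active only, equal all-randomised response, and early leaving counted as failure. The simulation also ignores the stratification of the planned test.

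The documents do not support saying that the primary result is biased towards volixibat, because they give neither the number of excluded subjects nor a difference between arms. Nor is a change to the Safety Analysis Set warranted: any visit, adverse event report or report of no events qualifies a dosed subject, and no effect of changing it has been shown. The change to the primary set is worth making because it costs so little and removes the question.

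**What to change.** In Sections 9.7, 9.8 and 9.8.1, assign the primary analysis and the binary NASH-resolution analysis to the Randomized Set, by assigned arm, for the doses continued after the interim analysis, with every missing Week 48 result counted as non-response. Keep the FAS as a sensitivity analysis, and carry the same assignment into the SAP before unblinding. Leave the Safety Analysis Set as it is.

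The cost is wording only: no new data, visits or subjects, and power stays at about 80% with 81 per arm. The downside is that the observed response rates may come out slightly lower. If early loss does fall mainly on active drug and the drug does nothing for those who stay, the test is somewhat conservative (1.7% rather than 2.5% at 5% loss).
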